## GLOSSARY OF ABBREVIATIONS

AE	Adverse Event
ASR/DSUR	Annual Safety Report / Development Safety Report
BASEC	Business Administration System for Ethical Committees
CRF	Case Report Form
CTCAE	Common Terminology Criteria for Adverse Events
FADP	Federal Act on Data Protection (in German: DSG, in French: LPD, in Italian: LPD)
eCRF	electronic Case Report Form
FOPH	Federal Office of Public Health
GCP	Good Clinical Practice
HRA	Human Research Act (in German: HFG, in French: LRH, in Italian: LRUM)
ICH	International Conference on Harmonisation
ClinO	Ordinance on Clinical Trials in Human Research (in German: KlinV, in French: OClin, in Italian: OSRUM)
SAE	Serious Adverse Event

## 1 STUDY SYNOPSIS

Sponsor / Sponsor-Investigator	Name(s) and contact details of Sponsor / Sponsor-Investigator
Study Title	Impact of Semi-automated proposal and optimization of diagnoses and surgical procedures for precoding: a randomized controlled trial
Short Title / Study ID	Semi-automated Precoding
Protocol Version and Date	Version 2 (dated 24/05/2019)
Study Registration	Intended: https://clinicaltrials.gov/
Study Category and Rationale	Not applicable
Background and Rationale	In a DRG system, insufficient or incorrect coding negatively impacts reimbursement. Assuming the DRG system in use to be optimal, the quality and efficacy of treatment could be improved if reporting and demission are electronically controlled and adjusted to the DRG system in use. In the long term, a fair reimbursement might reduce the pressure on the staffing ratio and thus increase the patient safety.
Risk / Benefit Assessment	The participants are not exposed to any intervention. A more accurate reporting and a treatment more adherent to the pre-setting of the DRG system in use by specially trained physicians should not impose any risk to the participants.
Objective(s) and Endpoint(s)	
Primary endpoint:
 
 
• Total reimbursement per day of hospital stay
 
 
Secondary endpoints:
 
 
• Length of hospital stay
 
• Total reimbursement per case
 
• Case mix index
 
• Severity of perioperative complications
 
• Readmission rate (safety endpoint)
 

Study Design	monocentric, randomized two-arm un-blinded study
Statistical Considerations	Continuous data are analysed using non-parametric Mann-Whitney U-tests because of skewed distributions of the data. Categorical data will be analysed using Chi-square-statistics.
Inclusion- / Exclusion Criteria	All inpatients hospitalized at the department of surgery undergoing any surgical procedure not eligible for ambulant operation at the Kantonsspital St. Gallen are included. No exclusion of vulnerable patients is planned.
Number of Participants with Rationale	According to a simulation study, a total of 1200 patients and 600 patients per arm are needed to detect an increase of 5% in the reimbursement per day of hospital stay with a power of 90%.
Study Intervention	In the intervention arm, reporting and the time of demission are crosschecked and corrected by physicians with special awareness of the DRG system during the hospital stay (preliminary precoding).
Control Intervention	In the control arm the coding for DRG grouping is performed after the patient's demission. Reports are not screened for conformability to the DRG coding system.
Study procedures	In the intervention arm, reporting and the time of demission are crosschecked and corrected by physicians with special awareness of the DRG system during the hospital stay (preliminary precoding).
Study Duration and Schedule	Planned 06/2019 of First-Participant-In Planned 01/2020 of Last-Participant-Out
Investigator	[name], Department of Surgery, Kantonsspital St. Gallen, St. Gallen, Switzerland E-mail: [contact] [contact]

Study Centre(s)	Kantonsspital St. Gallen, St. Gallen, Switzerland
Data privacy	No additional data exceeding the routine clinical data are generated. The electronic processing of these routine clinical data will be performed in the clinical database of the surgical department which is password-protected. As an additional measure of data privacy, only physicians involved in the study will be granted access to the results of electronic data processing.
Ethical consideration	The intervention assessed in this study consists of measures of quality control based on the DRG grouping. All data used for this study are already available to every physician involved in the treatment. For patients who are in the treatment group, treatment and reports are more extensively controlled by physicians. Thus the risk to overlook faults in documentation or treatment is likely to be reduced. If a more close implementation of the DRG Grouping transfers into less severe morbidity, a potential benefit for the participant would result.
GCP Statement	This study will be conducted in compliance with the protocol, the current version of the Declaration of Helsinki, the ICH-GCP, the HRA as well as other locally relevant legal and regulatory requirements.

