## 3.2 Primary and secondary endpoints

### Primary endpoint

The primary endpoint is defined as the total reimbursement divided by the length of hospital stay including the entry and the demission day. Reimbursement per day was defined as the primary endpoint because it better reflects the ratio of costs and reimbursement in contrast to simple total reimbursement. When analysing the reimbursement in 2018, the distribution of total reimbursement per patient was extremely skewed. Hence, to achieve a reasonable power for statistical significance a high number of study participants would be needed.

The total reimbursement according to the DRG coding of each included patient will be provided by the financial department. At the end of the study the financial department will provide the total reimbursement for all included patients. The length of hospital stay of each patient will be extracted from the clinical database of the surgical department which is updated and monitored on a daily base. In cases of readmission within 18 days because of a related diagnosis the cases are aggregated.

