#### Sample size calculation

Sample size calculation was performed in a separate simulation study using the total reimbursement divided by the length of hospital stay for the surgical department of the Kantonsspital St. Gallen in 2018. Sample size estimation was based on a two-sided significance level of  $\alpha = 0.05$  and a power of 90%. The increase in reimbursement was assumed to be 5% in the intervention group. Furthermore, in 15% of patients a shortening of the length of stay by one day was assumed in the intervention group. Randomization was 1:1. A drop-out rate of 10% was assumed. Based on this assumptions, a total of 1200 patients (600 per group) would be needed

to prove a significant increase in the total reimbursement divided by the length of hospital stay. According to the case load in 2018, the recruitment period would last 6 months.

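### The synopsis claims 90% power for a 5% rise in reimbursement per day, but the simulation behind N = 1200 assumed a larger effect on that endpoint

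*Combined protocol and SAP*

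**What the plan says.** Section 1 (Study synopsis, number of participants) takes its sample size from a simulation study: "a total of 1200 patients and 600 patients per arm are needed". The aim that the synopsis attaches to this number is to "detect an increase of 5% in the reimbursement per day of hospital stay with a power of 90" per cent. It mentions no effect on length of stay.

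Section 5.1 (Sample size calculation) describes that simulation, with the same 1200 patients, 600 per group and 90% power. It lists two effects. The first is "The increase in reimbursement was assumed to be 5% in the intervention group". The second is "Furthermore, in 15% of patients a shortening of the length of stay by one day was assumed in the intervention group". With both in place, 1200 patients are said to be needed "to prove a significant increase in the total reimbursement divided by the length of hospital stay".

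Section 3.2 fixes the endpoint as a ratio: "The primary endpoint is defined as the total reimbursement divided by the length of hospital stay including the entry and the demission day".

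**The concern.** A shorter stay reduces the denominator of the primary endpoint and so raises reimbursement per day. Section 5.1 adds this to the 5% gain, while the synopsis gives the same N and power to 5% per day by itself. Both statements cannot be right, and no section reconciles them.

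The synopsis is the only place where the detectable effect appears as a percentage of the primary endpoint. A reader who relies on it, such as an ethics committee, will think the trial more sensitive than the simulation supports. A non-significant result could then be misread as evidence against a 5% gain per day. The split between the two components also matters: the hypothesis in Section 3.1 concerns coding and reimbursement, whereas part of the simulated power comes from earlier discharge.

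**Working it through.** **Inputs from the documents.** Two-sided α = 0.05, power 90%, 1:1 allocation, 10% drop-out, 1200 in total (Section 5.1); endpoint = reimbursement / length of stay (Section 3.2); Mann-Whitney test (statistical analysis plan in Section 5.1). The distributions of stay and of reimbursement per day are not given.

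**The plan's own figure.** N = 1200 cannot be reproduced without the 2018 data. Only the drop-out step can be checked: 1080 / 0.90 = 1200, so 540 evaluable patients per arm would be consistent with the stated total.

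**Direction.** Suppose every patient stays L days, reimbursement rises by 5%, and a random 15% leave one day earlier with no loss of reimbursement. The mean gain per day is then

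1.05 × (0.85 + 0.15 × L/(L−1)) − 1.

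Since L/(L−1) > 1 for any finite L, this always exceeds 5%. At L = 7 it is 1.05 × (0.85 + 0.175) − 1 = 7.6%. If the 5% in Section 5.1 is read as already per day, the shorter stay still comes on top of it, so the conclusion is the same.

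**Size, under assumptions.** On the log scale the combined shift is

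d = ln(1.05) + 0.15 × ln(L/(L−1)), with ln(1.05) = 0.04879.

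Set the spread so that 1200 patients give exactly 90% power for d. Power for 5% alone is then

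Φ(3.2415 × 0.04879/d − 1.96), where 3.2415 = 1.9600 + 1.2816.

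The SD and the evaluable n cancel, so it does not matter whether 540 or 600 per arm are analysed. The total N that would give 90% for 5% alone is 1200 × (d/0.04879)².

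Example, L = 7: d = 0.04879 + 0.15 × ln(7/6) = 0.04879 + 0.02312 = 0.07191. The combined effect is e^0.07191 − 1 = 7.5%. Power is Φ(2.199 − 1.960) = Φ(0.239) = 59.5%.

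| Common stay L (days) | d | Combined effect per day (geometric) | Power for 5% alone | Total N for 90% at 5% alone |
|---|---|---|---|---|
| 3 | 0.1096 | +11.6% | 30.3% | about 6060 |
| 5 | 0.0823 | +8.6% | 48.5% | about 3410 |
| 7 | 0.0719 | +7.5% | 59.5% | about 2610 |
| 10 | 0.0646 | +6.7% | 68.7% | about 2100 |
| 12 | 0.0618 | +6.4% | 72.5% | about 1930 |
| 20 | 0.0565 | +5.8% | 80.0% | about 1610 |

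**Checks with varying stays.** These also calibrate the spread to 90% for the combined effect.

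- Mann-Whitney simulation, rounded log-normal stays, random shortening: about 39% at a median stay of 4 days, 50–51% at 6 days and 66–67% at 10 days.
- Large-sample Mann-Whitney power over 76 scenarios (median stay 3 to 14 days; shortening at random, in the longer half, in the shorter half or among the longest 30%): 37% to 84%, with combined effects of +5.5% to +10.6%.
- Only the longest 15% shortened: about 70% to 86%, with effects as low as about +5.4%.

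No scenario reached 90%.

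**The case against.** The strongest reply is that Section 5.1, the controlling text, discloses both components, and that the synopsis is a one-sentence summary of it. No calculation in the documents is shown to be wrong, no interim decision uses the figure, and N stands. This is right about the scope, and the point is limited accordingly. It does not remove the error: the synopsis names a specific effect and a specific power, and that pairing is not the one simulated.

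A second reply is that the size rests on invented distributions. That also stands. The gap is mildest if only the longest stays are shortened, where power for 5% alone reaches about 86%. The 80% at 20 days in the table applies only if all patients have the same stay; skewed stays can pass 80% with a median of 14 days or less. Further, 1200 may have been rounded up. If combined power were really 95%, the closed form would give 69% rather than 59.5% at 7 days, and 81% rather than 72.5% at 12 days. The 5% may also be a group average rather than a uniform gain, which would change the power of a rank test. These possibilities move the size of the gap, and none is stated in the plan.

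Two other readings could close the gap: that 5% per day is the net result of both effects, or that earlier discharge costs enough reimbursement to offset the gain. Section 3.4 mentions lower length-of-stay limits, but Section 5.1 lists the shorter stay as a separate, additional assumption and states no such penalty.

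**Conclusion.** The concern holds. Taking the stated 90% as the power for the effect in Section 5.1, the synopsis attaches it to an effect smaller than the one simulated, and power for a 5% rise in reimbursement per day alone is below 90%. This needs no outside data, only that the shorter stay is added to the 5% without an offsetting loss of reimbursement, as Section 5.1 describes it.

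How far below cannot be derived from the documents. Under the assumptions shown, the range is about 30% to 86%, with a combined effect between about +5.4% and +11.6% per day on the geometric scale. The fault is an incorrect summary figure. It does not show that 1200 is wrong for the Section 5.1 scenario, and it does not touch the test or the conduct of the trial. It should be corrected.

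**What to change.** Restate the synopsis so that 600 patients per arm are tied to 90% power for the combined effect: 5% more total reimbursement (if that is what was simulated) and a one-day shorter stay in 15% of intervention patients. Give the equivalent percentage rise in reimbursement per day, taken from the existing 2018 simulation, and say how it is averaged. The choice matters for short stays: at 3 days the geometric figure is +11.6% and the arithmetic figure +12.9%.

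Beside it, report the power for a 5% rise per day alone, from a re-run of the same simulation with the length-of-stay component switched off.

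Copying the two assumptions into the synopsis would cure the contradiction by itself; the re-run tells the reader what the trial can detect at 5%. It would also help to add a sentence to Section 5.1 on which patients were shortened and how the shortest stays were handled, though the correction does not depend on it.

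The cost is one re-run of existing code, one corrected synopsis sentence and one optional sentence in Section 5.1. N does not change. The only drawback is a less favourable stated power for 5% per day.

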## 2 BACKGROUND AND RATIONALE

Increasing cost pressure on health care providers in combination with further developments in reimbursement systems over the past decades led to reductions of staffing ratio with possible negative consequences on patients' safety in hospital environments. Diagnosis-related group (DRG) as a system to classify hospital cases was intended to identify "the products" that a hospital provides. DRG systems are widely spread in the world and used for reimbursement since the early 1970s. In the United States of America, the system was developed to use it explicitly for reimbursement in 1982. Roughly, DRGs are assigned by a "grouper" program based on the International Classification of Diseases (ICD) diagnoses and procedures, age, sex, discharge status, and the presence of complications or comorbidities. In a DRG system insufficient or incorrect ICD coding directly leads to a negative impact on reimbursement which may increase the pressure on staffing ratio again. This leads to a negative spiral with potentially impaired patient safety. Complications and comorbidities are at risk of both, underrecognition and incomplete coding. Furthermore, in surgery chronic diagnoses are often coded insufficiently. This may be a barrier of proper diagnosis and consequently optimal treatment strategies for the individual patient. Another barrier may include the perception that some specific diagnoses are not essential to make or code because "nothing can be done" or because it is not considered relevant for the actual medical problem [1]. The ICD is a defined list of diagnoses that are used for standardized diagnoses coding. The CHOP Code Catalogue is the official Swiss catalogue of medical treatments. Both coding systems are the basis for DRG coding in Switzerland and accordingly in many other countries with different catalogues of medical treatment. Besides the actual DRG code, it seems that further factors like quality of documentation and medical coding influence the financial proceeds of a hospital case [2–7].

Therefore the main aim of present project is to determine if daily monitoring and optimization of DRG coding of individual cases lead to better reimbursement.

## 3 STUDY OBJECTIVES AND DESIGN

### 3.1 Hypothesis and primary objective

The hypothesis of present study is that the daily monitoring and optimization of DRG coding is associated with higher reimbursement. Therefore, the primary objective is to determine if the daily monitoring and optimization of DRG coding of individual cases leads to better proceeds per day.

### Secondary objectives:

Comparing the following parameters with and without daily monitoring and optimization of DRG coding:

1. Length of hospital stay including entry and demission date
2. Total reimbursement per case
3. Case mix index
4. Severity of perioperative complications
5. Readmission rate

## 3.2 Primary and secondary endpoints

### Primary endpoint

The primary endpoint is defined as the total reimbursement divided by the length of hospital stay including the entry and the demission day. Reimbursement per day was defined as the primary endpoint because it better reflects the ratio of costs and reimbursement in contrast to simple total reimbursement. When analysing the reimbursement in 2018, the distribution of total reimbursement per patient was extremely skewed. Hence, to achieve a reasonable power for statistical significance a high number of study participants would be needed.

The total reimbursement according to the DRG coding of each included patient will be provided by the financial department. At the end of the study the financial department will provide the total reimbursement for all included patients. The length of hospital stay of each patient will be extracted from the clinical database of the surgical department which is updated and monitored on a daily base. In cases of readmission within 18 days because of a related diagnosis the cases are aggregated.

### Secondary endpoints

1. Length of hospital stay: The number of days of the hospital stay including the entry and the demission day will be extracted from the clinical database of the surgical department
2. Total reimbursement per case: At the end of the study a list of included patients will be sent to the financial department. Based on this list, the financial department will provide the total reimbursement per case measured in Swiss Francs.
3. Case mix index: At the end of the study a list of included patients will be sent to the financial department. Based on this list, the financial department will provide the effective cost weight of each patient.
4. Severity of perioperative complications: The severity of perioperative complications are already routinely recorded applying the Clavien-Dindo-Classification. This standardized classification is chosen to ascertain external and internal comparability. Perioperative complications of all operated patients are routinely recorded by a dedicated physician and stored in the clinical database of the surgical department.
5. Readmission rate: On a daily basis, all admissions and readmissions are routinely presented and discussed during the morning meeting of the surgical clinic. The list of readmissions will be cross checked with the randomisation list and the demission of the included patients.

## 3.3 Study design

This is a monocentric, randomised two-arm un-blinded study.

## 3.4. Study intervention

First, based on the randomisation list, for all patients randomized into the group with daily monitoring and optimization of DRG coding (treatment group), dedicated physicians control if all relevant diagnoses and procedures are correctly coded in the operation management software. If necessary, additional codable diagnoses and procedures are discussed with the operating surgeon and if appropriate the coding is changed accordingly. Finally, the internal coherence of the coding and the wording of the operation report are crosschecked. Therefore, the electronic signature procedure of operation reports will be adopted such that the report will not be sent before one of the dedicated physicians approved its final version.

Second, the dedicated physicians control if relevant diagnoses and procedures are correctly recorded in the drafts of the discharge reports. Therefore, patients in the treatment group are visited daily. In addition, the patient records are inspected and their relevance for the DRG coding is assessed. If necessary, relevant diagnoses are incorporated in the draft of the discharge report. Additionally, the matching between diagnoses and procedures listed in the discharge report is crosschecked. The optimal time of discharge of each patient is evaluated on a daily base.

To support the process described above, for all patients randomized into the group with daily monitoring and optimization of DRG coding (treatment group), a pdf file with the current DRG grouping according to the procedures and diagnoses routinely coded in the Operation management software is created. Based on these procedures and diagnoses, the current DRG grouping status is estimated. Based on the estimated DRG grouping status, the actual length of stay is compared with the lower and upper limit and the mean length of stay determined by the associated actual DRG group. Additionally, based on routinely and systematically collected data in the clinical database of the surgical department, potential secondary diagnoses relevant for reimbursement are generated by computerized algorithms. For each potential secondary diagnosis, the hypothetical DRG Grouping considering the already coded procedures and diagnoses is estimated. The possible secondary diagnoses are deducted from laboratory measurements, from the extended Charlson comorbidity score routinely evaluated preoperatively by the department of anaesthesiology, and from the recording of perioperative complications.

Third, final discharge reports of patients randomized into the group with daily monitoring and optimization of DRG coding (treatment group), are controlled to ascertain the completeness of diagnoses and procedures and their concordance. Therefore, the electronic signature procedure of discharge reports will be adopted such that the report will not be sent before one of the dedicated physicians approved its final version.

In patients randomized into the control group none of the above described intervention steps will be performed. In these patients, the actual clinical routine will apply.

## 4 STUDY POPULATION AND STUDY PROCEDURES

### 4.1 Inclusion and exclusion criteria, justification of study population

All patients undergoing any elective or emergency surgical procedure not eligible for ambulant operation at the Kantonsspital St. Gallen, Department of Surgery are eligible for study. All patients screened for the trial are documented in the screening log. Patients meeting the inclusion criteria are enrolled in the trial.

